### **8.3. Software**

The PK parameters will be derived using Phoenix WinNonlin® version 8.3 or higher (Certara, L.P.). SAS® 9.4 or higher (SAS institute, Inc., Cary, NC USA) will be used for PK statistical analysis to provide tables, listings, and figures.

### **8.4. Handling of Missing Values/Censoring/Discontinuations**

The following imputation method will be applied for subjects with missing data:

- Subjects who lose their graft will be assigned a value of zero for their missing estimated glomerular filtration (eGFR) value.
- Subjects who die or are lost to follow-up with a functioning graft will have an imputed value using the last-observation-carried-forward (LOCF) method.
- For subjects that discontinue randomized treatment, the eGFR will be considered missing after applying the windows.

Graft loss subjects do not have a functioning graft; hence the lowest possible GFR value (zero) will be assigned to such subjects. In contrast, subjects that die with a functioning graft, die for different reasons (e.g., suicide, car accident, cancer) will have an imputed value assigned as described above.

Subjects who are lost to follow-up have renal function, but missing values for various reasons (e.g., moving from the area or not being able to make the site visit during the Month 6 or Month 12 visit window).

Subjects who have a functioning graft at the time of death or are Lost to Follow-up with a functioning graft will be analyzed via an imputation method that employs LOCF.

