Following transplantation, subjects should be treated post-operatively per standard-of-care clinic practice and per the assessments outlined in the protocol. Following discharge from the hospital and unless more frequent clinic visits are required for laboratory specimen collection, subjects will present to the clinical site for study visits weekly up to and including Week 10 and then monthly through Month 12 or EOS, and as outlined per the Schedule of Assessments outlined in Appendix 1.

All randomized subjects are expected to continue in the study up to Month 12 regardless of being on or off assigned treatment. Subjects who are randomized but not transplanted or administered their first dose of siplizumab will be replaced.

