# 9.1.2 Discontinuation of Study Treatment

Discontinuation of study treatment for a subject occurs when study treatment is stopped earlier than the protocol planned duration. Discontinuation can be initiated by the subject, the investigator, or by ITB-MED.

Possible reasons for study treatment discontinuation are:

- AE, e.g., cytokine release syndrome, PTLD, CTS
- Lack of Efficacy
- Technical problem during transplant surgery
- Primary non-function
- Subject/Guardian Decision
- Lost to follow-up
- Pregnancy
- Death
- Graft Loss

The Investigator should discontinue a subject from their randomized treatment regimen if he/she believes that continuation in the study would be detrimental to the subject's well-being.

Subjects who discontinue their study treatment should NOT be considered withdrawn from the study UNLESS they withdraw their consent to participating in all the elements of the study. Such subjects should remain in the study, if possible, and receive standard of care immunosuppression, according to local practice, and return for follow-up visits through Month 12.

All randomized subjects are expected to continue in the study up to Month 12. If they refuse to return for these assessments or are unable to do so, every effort should be made to contact them to

determine their health status, evaluate safety (SAEs) and to request a final study visit. Documentation of attempts to contact the subject should be recorded in the source documentation. If the subject is unable to return for a final study visit, every effort to obtain the subject and graft status should be made and documented within the subject chart.

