# 12.4.3 Handling of Missing Values/Censoring/Discontinuations

The analysis will be made on the FAS population. The following imputation method will be applied for subjects with missing data:

- Patients that lose their graft will be assigned a value of zero for their missing estimated glomerular filtration (eGFR) value.
- Patients that die or are lost to follow-up with a functioning graft will have an imputed value using the last-observation-carried-forward (LOCF) method.
- For subjects that discontinue randomized treatment, the eGFR will be considered missing after applying the windows defined in Section 12.1.

Graft loss subjects do not have a functioning graft; hence the lowest possible GFR value (zero) will be assigned to such subjects. In contrast, subjects that die with a functioning graft, die for different reasons (e.g., suicide, car accident, cancer) will have an imputed value assigned as described above.

Patients who are lost to follow-up have renal function, but missing values for various reasons (e.g., moving from the area or not being able to make the site visit during the Month 6 or Month 12 visit window). Patients who have a functioning graft at the time of death or are Lost to Follow-up with a functioning graft will be analyzed via an imputation method that employs LOCF.

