### **7.2. Full Analysis Set**

The Full Analysis Set (FAS) comprises all subjects to whom study treatment has been assigned by randomization. According to the intent-to-treat principle, subjects will be analyzed according to the treatment they have been assigned to during the randomization procedure.

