### **8.2. Definition of Baseline**

Unless otherwise stated, the last observed measurement prior to or on the date of first study medication will be considered the baseline measurement.

For eGFR analysis (See Section **Error! Reference source not found.**), the baseline will be based on the Week 4 assessment.

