### 11.6. Renal Function

- **Change from baseline in renal function eGFR**

Renal function will be assessed by eGFR, using an automated calculation factoring serum creatinine, demographics and the MDRD4 formula.

MDRD 4-variable GFR Equation as below:

$$GFR \text{ in } mL/min \text{ per } 1.73 \text{ } m^2 = 175 \times \text{SerumCr}^{-1.154} \times \text{age}^{-0.203} \times 1.212 \text{ (if patient is black)} \\ * 0.742 \text{ (if female)}$$

- **Change from baseline in CKD-EPI**

The CKD-EPI equation are modeled using least squares linear regression to relate log transformed measured GFR to log-transformed filtration markers, age and sex with two slope splines for creatinine, Expressed as a single equation:

$$eGFR = 142 * \min(\text{standardized Scr/K, 1}) \alpha * \max(\text{standardized Scr/K, 1}) \\ - 1.200 * 0.9938 \text{Age} * 1.012 \text{ [if female]}$$

Abbreviations / Units:

*eGFR (estimated glomerular filtration rate) = mL/min/ 1.73 m^2*

*Scr (serum creatinine) = mg/dL*

*K = 0.7 (females) or 0.9 (males)*

*$\alpha = -0.241$  (females) or  $-0.302$  (males)*

*min = indicates the minimum of Scr/K or I*

*max = indicates the maximum of Scr/K or I*

The above parameters will be summarized by visit. This will also be evaluated at Months 3, 6 and 12 (EOS) by comparing the mean eGFR values between groups.

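### eGFR collected after a subject stops randomized treatment is set to missing, so followed subjects drop out of the between-group mean eGFR comparison

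*SAP*

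**What the plan says.** SAP 8.4 gives three rules for eGFR. Graft loss is scored zero. Death or loss to follow-up with a functioning graft is handled by last observation carried forward (LOCF). The third rule reads: "For subjects that discontinue randomized treatment, the eGFR will be considered missing after applying the windows". Protocol 12.4.3 has the same three rules and adds a location for the windows: "the eGFR will be considered missing after applying the windows defined in Section 12.1". It also names the population: "The analysis will be made on the FAS population". SAP 7.2 defines that population by assignment: "According to the intent-to-treat principle, subjects will be analyzed according to the treatment they have been assigned to during the randomization procedure".

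The values feed two summaries in SAP 11.6. One is change from baseline, where SAP 8.2 says "the baseline will be based on the Week 4 assessment". The other is a comparison across arms: "This will also be evaluated at Months 3, 6 and 12 (EOS) by comparing the mean eGFR values between groups". Protocol Table 2-1 lists eGFR by MDRD among the endpoints for the primary objective. SAP 4.1 lists it as secondary.

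On follow-up, Protocol 3.1 says: "All randomized subjects are expected to continue in the study up to Month 12 regardless of being on or off assigned treatment". Protocol 9.1.2 says: "Subjects who discontinue their study treatment should NOT be considered withdrawn from the study", the exception being withdrawal of consent. Protocol 6.4.2 likewise keeps subjects who leave the study regimen in the trial to Month 12.

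**The concern.** The protocol follows subjects after they stop treatment, and the third rule then discards the eGFR that follow-up yields. That does not fit an all-randomized population, and it treats observed data worse than absent data: a lost subject contributes a carried-forward value, while a subject who attends Month 12 off treatment contributes nothing.

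Induction is short (siplizumab on Days 0 and 4, rATG on Days 0 to 2). If *randomized treatment* means the induction agent, anyone who stops it early does so before every eGFR time point in the analysis, including the Week 4 baseline. If it also covers tacrolimus, MMF and corticosteroids, more subjects can be affected, and they too are followed to Month 12.

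What is at stake is bias in the arm means. Stopping can be related to the kidney: Protocol 9.1.2 lists lack of efficacy and primary non-function among the reasons. Protocol 6.7.3 requires the investigational product to be discontinued when a polyclonal antibody or rATG is used for delayed graft function before Day 4. The Synopsis names siplizumab as the investigational product, so that forced stop has no evident counterpart in the rATG arm. Removing poorly functioning kidneys from a siplizumab arm would flatter it. The trial tests no hypothesis, so power and type I error are not at issue. However, Protocol 1.2 says the results will inform later dose selection, and Protocol 4.2 says the comparative data will help estimate effect size.

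**Working it through.** The documents give no eGFR standard deviation, expected mean or discontinuation rate, so there is no planned figure to reproduce. The check has two parts.

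**1. Which values would be lost.** The answer depends on the windows. Protocol 12.1, the section cited, defines only analysis sets. SAP 8.4 drops the cross-reference and supplies no windows. Three candidate periods appear elsewhere, none linked to this rule:

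| Candidate | Source | Effect on a subject stopping after one dose on Day 0 |
|---|---|---|
| Visit windows | Protocol Appendix 1 | These bound visit timing only. If every value after the stop is missing, Week 4 (Day 28) and Months 3, 6 and 12 (Days 84, 168, 336) are all lost |
| Last dose minus first dose plus 40 days | SAP 10.1.1 | Ends about Day 0 + 40 = Day 40. Week 4 is kept; Months 3, 6 and 12 are lost |
| First dose to Month 12 or end of study | Protocol 12.5.2, for safety summaries | Nothing to Month 12 is lost, so the rule has no effect there |

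Under the first two, the subject leaves the between-group comparison at all three time points.

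**2. How far an arm mean moves.** Inputs: 8 subjects per arm (SAP 8, General Conventions, with rATG pooled as 4 + 4). Assumed for illustration: seven subjects at 55 mL/min/1.73 m² and one discontinuer with a functioning graft at *x*.

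Mean with all values = (7 × 55 + *x*)/8. Mean after deletion = 55. Shift = 55 − (385 + *x*)/8 = (55 − *x*)/8.

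| *x* | Mean, all values | Mean after deletion | Shift |
|---|---|---|---|
| 10 | 49.375 | 55 | +5.625 |
| 25 | 51.25 | 55 | +3.75 |
| 40 | 53.125 | 55 | +1.875 |
| 55 | 55 | 55 | 0 |
| 70 | 56.875 | 55 | −1.875 |

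*Same kidney, two rules.* A subject last seen at 25 and then lost to follow-up is carried forward, giving an arm mean of 51.25. The same subject still at 25, off treatment and attending Month 12, is deleted, giving 55.0.

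*With a graft loss kept at zero.* Six at 55, one discontinuer at 25 and one graft loss: all values give (330 + 25 + 0)/8 = 44.375. The rule gives (330 + 0)/7 = 47.143, a shift of +2.768. If the missing rule overrode the zero as well, the mean would be 330/6 = 55. The documents do not say which rule governs.

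*Chance of it arising.* At assumed, independent discontinuation rates of 5%, 10% and 20%, the chance that at least one of 24 subjects is affected is 1 − (1 − *p*)^24 = 71%, 92% and 99.5%. Within one arm of 8 it is 34%, 57% and 83%.

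**The case against.** The strongest reply is that SAP 8.4 introduces all three rules as imputation for subjects with missing data. On that view the third rule only says that values absent after discontinuation stay missing instead of being carried forward. The wording permits this reading but does not state it. A value that was never collected does not need windows to be considered missing, so reclassification of collected values is the plainer sense. If the benign meaning was intended, the text still has to say so.

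Second, the on-treatment period in Protocol 12.5.2 would leave all values to Month 12 intact. That is correct, but the rule does not refer to that period, and adopting it would leave the rule with nothing to do up to Month 12.

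Third, the intent-to-treat sentence governs the arm in which a subject is counted, not which time points are used. Also, SAP 11.6 names no analysis set, and a line in SAP 7.4 and Protocol 12.1 says all sets are analysed by treatment received. These points stand as limits: the FAS attribution comes from Protocol 12.4.3, and the treatment-received line conflicts with the FAS definition. Neither restores a deleted value.

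Fourth, Protocol 6.7.3 also allows study treatment to be interrupted or reduced for delayed graft function without restriction by arm, so rATG subjects may be affected too. The forced stop is the more specific route, but the net direction is unknown.

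Finally, the analysis is descriptive, and the raw values remain in listings and Safety Set laboratory summaries. That limits the harm but does not correct the means in SAP 11.6. The exploratory eGFR section (SAP 12.4.1) is redacted and cannot be assessed.

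**Conclusion.** The concern holds. On the plain reading, eGFR collected under the protocol is excluded from the between-group means at Months 3, 6 and 12 because a subject stopped treatment. On the strictest reading the Week 4 baseline goes too. One deleted subject moves an arm mean by (55 − *x*)/8 under the assumed values: about +5.6 to −1.9 mL/min/1.73 m² for *x* from 10 to 70. The direction depends on who stops. The delayed-graft-function route could favour siplizumab, while non-renal stops may push either way. The size rests entirely on assumed eGFR values, and the frequency on assumed rates. The textual defects rest on no assumption: *randomized treatment* is undefined for this rule, the window reference leads nowhere, and the three rules can apply to one subject without a stated order. Protocol 9.1.2 lists death, loss to follow-up, graft loss and primary non-function as reasons for discontinuing, so such overlap is to be expected. This should be fixed before the final analysis.

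**What to change.** In SAP 8.4, replace the third rule with a statement that all observed eGFR to Month 12 is summarised in the FAS by assigned arm, whether or not treatment was discontinued. Name that population in SAP 11.6, and state that the treatment-received line in SAP 7.4 does not apply to this summary. State that zero for graft loss, including primary non-function (recorded on the Graft Loss eCRF under Protocol 6.7.4), takes precedence over the other rules.

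Any on-treatment version should be a sensitivity summary only, with *randomized treatment* and its windows defined. Replace the reference to windows in Protocol 12.1 with defined analysis windows, for example built on the visit windows in Appendix 1.

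The cost is a SAP revision before database lock or, failing that, a deviation recorded in the clinical study report, as SAP 3 allows. Protocol 12.4.3 can be aligned at the next amendment. No extra subjects, visits or data are needed.

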## **9. DESCRIPTION OF THE ANALYSIS POPULATION**

Summary statistics will be presented for the subjects in the FAS.

Continuous variables will be presented with mean, median, 25th percentile, 75th percentile, standard deviation (SD), minimum and maximum, and the number of non-missing observations.

Categorical data will be displayed via absolute and relative frequencies for each category (including a category labeled as “missing” when appropriate).

### **9.1. Disposition**

Subject disposition summaries will be presented by treatment arm and will include the number of subjects randomized, the number and percentage of randomized subjects in each analysis populations, as well as the number and percentage of subjects who complete the study. The summaries will also include the reasons for early discontinuation from the study.

The table format will be similar to the disposition table presented to the DMC.

Data for disposition variables will be presented in a listing by treatment arm and subject.

### **9.2. Demographic and Baseline Characteristics**

Demographic summaries will be provided by treatment arm and will include age, sex, race, ethnicity, height, weight, and BMI. These summaries will be presented for the subjects in the Full Analysis Set (FAS) and Safety set (SS).

Data for demographic variables will be presented in listings by treatment arm and subject.

### **9.3. Other baseline characteristics**

Other baseline disease characteristics include relevant medical history, transplant history, other concomitant procedures, childbearing potential, donor characteristics (e.g., age, sex, race, type, CIT) and any other relevant information.

Medical history and procedures will be coded by MedDRA (Medical Dictionary for Regulatory Activities, version 26.0 or higher). Medical history will be summarized according to System Organ Class (SOC) and Preferred Term (PT).

Medical history, current medical conditions, results of laboratory screens, transplant history, donor characteristics will be presented in listings by treatment arm and subject respectively.

### **9.4. Prior and Concomitant Medications**

All medications recorded on the CRFs will be coded using the WHODrug Dictionary (version March 2023 or higher). Prior and concomitant medications will be summarized by treatment arm in the Safety Set by anatomical therapeutic chemical (ATC) Class Level 4 and WHODrug base substance preferred name.

Prior medications are defined as medications with stop dates occurring before the date of first administration of any study treatment. Concomitant medications are defined as medications with start dates occurring on or after the date of first administration of any study treatment and no more than 30 days after the last study visit. Medications with start and stop dates that bracket the date of first administration of a study treatment will be summarized as both prior and concomitant medications.

Medications that were stopped prior to the date of first administration of a study treatment will be included in the prior medications table, and medications that were started on or after the date of first administration of any study treatment component will be included in the concomitant medications table. All other medications will be included in both the prior and concomitant medications tables if the date they were started or stopped is unclear.

Prior and concomitant medications will be summarized for the Safety Set.

Prior and concomitant medications will be presented in listings.

#### **9.4.1. Concomitant Immunosuppressants**

The average daily dose of administered TAC, MMF, and CS will be summarized by treatment arm for subjects receiving study medication. The dose of the induction agent will be summarized for each of days when it was administered.

The dose of antibodies used for the treatment of acute rejection episodes will be recorded as well. TAC, MMF, and CS administration and average daily dose will be presented in listings.

#### **9.4.2. Other Concomitant Medications**

Concomitant medications, other than immunosuppressants and CS mentioned above, will be summarized by therapeutic class and preferred term by presenting the number and percentage of subjects using each medication for each treatment group.

Information for other co-medications will be presented in listings.

### **10. ANALYSIS OF PRIMARY ENDPOINTS**

#### **10.1. Safety Analysis**

Safety analyses will be performed using the Safety Set. Assessment of safety will be based on the incidence, severity, relatedness, and type of adverse events, as well as on clinically significant changes in the subject's physical examination, and vital signs. Safety variables will be tabulated and presented by study drug received.

Because there is no pre-specified safety outcome defined in terms of AEs or vital signs, any formal comparisons between the treatment arms with respect to specific safety parameters will be *post hoc*.

##### **10.1.1. Extent of Exposure**

Summary statistics of exposure to study drug will be tabulated by treatment arm. The exposure will be summarized using duration and average dosing. Duration of exposure is defined as last

Confidential

Page 18 of 28

dosing date – first dosing date + 40; e.g. 5 PK half-lives. Exposure by average dose is defined as X/Y, where X is the total dose received and Y is planned number of doses to be given.

The duration (days) of study medication administration will be summarized. This will be calculated by subtracting the date of the last administration of study medication from the date of first administration and then adding the dosing interval for Siplizumab, TAC, MMF or CS. In calculating the duration of treatment, days of temporary interruption of study medication for any reason will be included. Further, the frequency of dose changes (including temporary dose interruption) will be presented by reason for the change.

Average daily doses will be presented by treatment. “Zero” will be used for periods of temporary interruption of study medication for any reason.

The number and percentage of subjects who prematurely discontinued study medication will be summarized by reason for discontinuation.

Study treatment errors, including uses outside of what is foreseen in the protocol, will be summarized. AEs as a result of study treatment error will also be summarized.

Extent of exposure data will be presented in a listing.

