Preliminary modeling of the limited PK/PD data available in renal transplant patients and T-cell lymphoma patients suggests a strong population effect on the pharmacokinetics of siplizumab (MEDI-507). In renal transplant patients, the apparent PK half-life  $(T_{1/2})$  is 8.5 days. In lymphoma patients, where there is an abundance of CD2+ lymphocytes and CD2 target to which siplizumab can bind, a higher clearance and shorter  $T_{1/2}$  has been estimated of approximately 4.75 days. The primary difference is inflection point concentration at which linear clearance transitions to a more rapid clearance. In T-cell lymphoma patients, this transition occurs at a concentration ~40-fold higher (15 µg/mL) than renal transplant patients (0.35 µg/mL).

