#### 6.2.3 **Investigational Product Dosing Regimen**

The starting dose for siplizumab will be 0.2 mg/kg with escalation to 0.6 mg/kg.

The planned duration of investigational treatment is 5 days. Subjects will receive a total of two doses of siplizumab: pre- or intra-operatively on Day 0 and on Day 4. Subjects may be discontinued from treatment earlier at the discretion of the investigator or upon request of the subject.

Siplizumab dose adjustments and/or interruptions for a given subject are not permitted. The siplizumab infusion rate may be changed in the event of an infusion reaction.

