#### 12.3 **Treatments**

The duration (days) of study medication administration will be summarized. This will be calculated by subtracting the date of the last administration of study medication from the date of first administration and then adding the dosing interval for siplizumab, TAC, MMF or CS. In calculating the duration of treatment, days of temporary interruption of study medication for any reason will be included. Further, the frequency of dose changes (including temporary dose interruption) will be presented by reason for the change.

Average daily doses will be presented by treatment. "Zero" will be used for periods of temporary interruption of study medication for any reason.

The number and percentage of subjects who prematurely discontinued study medication will be summarized by reason for discontinuation.

Study treatment errors, including uses outside of what is foreseen in the protocol will be summarized. AEs as a result of study treatment error will also be summarized.

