## 5. INTERIM ANALYSIS

### 5.1. Interim Analysis Objectives

A formal interim analysis was conducted when 50% of subjects in Cohort 1 and 2 completed their 6-month study assessment according to a separate interim analysis plan (dated 03MAR2023). This formal interim analysis was conducted to assess the safety/tolerability (e.g., AEs, SAEs, clinical laboratory assessments, vital signs, PK data and PK/PD activity [e.g., immunophenotyping and CD2 receptor occupancy]). The analysis also included assessment of biopsy proven acute rejection (BPAR), graft losses deaths, and key safety endpoints. In the event the acute rejection rate exceeds a clinically relevant threshold set forth in the protocol and DMC charter, or the a priori defined stopping rules, enrollment were to be suspended to allow for the early termination of any treatment cohort where the benefit/risk of Siplizumab was deemed unacceptable.

The following treatment arms will be utilized for TCD601B102:

- Arm 1: Siplizumab 0.2 mg/kg (n=8 in Cohort A)
- Arm 2: Siplizumab 0.6 mg/kg (n=8 in Cohort B)
- Arm 3: rATG, a control arm, (n=4 each in Cohort A and B)

Subjects randomized to Siplizumab will receive two intravenous (IV) doses on Day 0 and Day 4 post-transplant and subjects randomized to rATG (Arm 3) will receive three intravenous (IV) doses of 1.5 mg/kg on Days 0, 1, and 2, regardless of Cohort assignment.

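### The SAP's rule for duration of administration subtracts the dates in the wrong direction, and rATG is not properly covered by either duration rule

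*SAP*

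**What the plan says.** SAP section 10.1.1 (Extent of Exposure) contains two duration rules.

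- **Duration of exposure.** The sentence begins with the word last and, across a page break, continues "dosing date – first dosing date + 40; e.g. 5 PK half-lives". It applies to exposure to study drug, summarised by arm. Nothing limits it to siplizumab.
- **Duration of administration.** The next paragraph reads "This will be calculated by subtracting the date of the last administration of study medication from the date of first administration", and the sentence goes on to "then adding the dosing interval for Siplizumab, TAC, MMF or CS". rATG is not in that list.

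Protocol section 12.3 has the second rule in the same form ("subtracting the date of the last administration of study medication from the date of first administration and then adding the dosing interval") but no 40-day rule. The SAP does not say how the two durations relate, and neither document gives a number for the siplizumab dosing interval.

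The schedule is clear. For siplizumab, SAP section 5.1 says "Subjects randomized to Siplizumab will receive two intravenous (IV) doses on Day 0 and Day 4 post-transplant", and protocol section 6.2.3 adds: "The planned duration of investigational treatment is 5 days". rATG is given on Days 0, 1 and 2 (protocol section 6.3.1).

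**The concern.** Subtracting the last date from the first gives a negative number for any course longer than one day. Adding one dosing interval cannot rescue it for a drug taken for months. The same rule ranks siplizumab subjects backwards, because someone who stops after the first dose is credited with more time than someone who completes the course.

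The 40-day constant raises a different question. It is explained by PK half-lives, and PK parameters are planned for siplizumab only, yet the rule is written for study drug in general and reported by arm. Taken at face value, it gives the rATG control arm a tail that belongs to another drug.

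Extent of exposure sits under the primary safety analysis. SAP section 3 says the document exists to set out derivations, that the approved plan governs the final analysis, and that departures are to be noted in the study report. A silent correction by the programmer would therefore be an undocumented departure, and it would still need a guess at the siplizumab interval and at the rule for rATG.

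**Working it through.** **Inputs**

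- Siplizumab: first dose Day 0, last dose Day 4 (SAP 5.1). Planned duration 5 days (protocol 6.2.3). Interval not stated; 4 days is assumed because it is the gap between the two doses, and 1 and 5 days are shown as a range.
- rATG: Days 0 to 2 (protocol 6.3.1).
- Tacrolimus and MMF: twice daily, so 0.5 day (protocol 6.4.1 and 6.4.2).
- Corticosteroid: a minimum daily dose from Day 0 to Month 12 (protocol 6.4.3). The interval is taken as 1 day.
- Month 12: 12 × 28 = Day 336 (protocol section 8 and the schedule of assessments).

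**The plan's own figure.** The planned 5 days for siplizumab is an inclusive count: last − first + 1 = 4 − 0 + 1 = 5.

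**Administration rule as written: first − last + interval**

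| Course | Calculation | As written | With last − first |
|---|---|---|---|
| Tacrolimus or MMF, Day 0 to 336 | 0 − 336 + 0.5 | −335.5 | 336.5 |
| Same, started on Day 1 | 1 − 336 + 0.5 | −334.5 | 335.5 |
| Tacrolimus stopped at Day 28 | 0 − 28 + 0.5 | −27.5 | 28.5 |
| Corticosteroid, Day 0 to 336 | 0 − 336 + 1 | −335 | 337 |
| Siplizumab, both doses, interval 4 | 0 − 4 + 4 | 0 | 8 |
| Siplizumab, both doses, interval 1 | 0 − 4 + 1 | −3 | 5 |
| Siplizumab, both doses, interval 5 | 0 − 4 + 5 | +1 | 9 |

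The result is negative whenever the course is longer than one interval, so the sign for tacrolimus, MMF and corticosteroid does not depend on the interval chosen. For siplizumab with interval τ, one dose gives τ and two doses give τ − 4. The completer is therefore always 4 days below the early stopper.

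**Exposure rule as written: last − first + 40**

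- Siplizumab, both doses: 4 − 0 + 40 = 44 days.
- rATG: 2 − 0 + 40 = 42 days, against an inclusive dosing span of 2 − 0 + 1 = 3 days.

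The arms would read 44 and 42 days where the dosing spans are 5 and 3.

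**The case against.** The best defence is that this is a slip of wording. The exposure rule, one paragraph earlier, has the direction right, adding a dosing interval makes sense only after last minus first, and durations near −335 days would be noticed at once in the table or listing. That is probably so, and it limits the practical risk. It does not supply the missing siplizumab interval or a rule for rATG.

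A second defence is that the two durations have different names. One may be a pharmacological window and the other the time over which drug was given. This stands. A reader might see 44 days beside 0 (or 8 with the direction corrected) and infer that the SAP contradicts itself. The documents do not support that, since two measures may properly differ. The fair complaint is that their relation is not stated.

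Third, the 40 days is tied to PK half-lives, so it may have been meant for siplizumab only. That is a plausible intention, but the section does not say it. The 42 days for rATG is what the text yields, not a demonstrated output.

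Fourth, little depends on these durations. SAP section 10.1 rests the safety assessment on adverse events, physical examination and vital signs. The adverse event tables are counts and percentages, and protocol section 12.5.2 defines the on-treatment period independently. This stands in full.

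Last, adding 1 day instead of a dosing interval departs from the protocol's convention. That is fair: any stated constant would do.

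**Conclusion.** The administration rule is reversed in both SAP 10.1.1 and protocol 12.3. Followed literally, it gives about −335.5 days for tacrolimus or MMF and about −335 for corticosteroid over the full study. These signs need no assumption beyond treatment lasting longer than one interval. The 0 days for a full siplizumab course is conditional on an assumed 4-day interval and runs from −3 to +1 over intervals of 1 to 5 days. rATG is missing from the administration rule, and as written the exposure rule gives it 42 days for a 3-day course.

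The effect is confined to the descriptive exposure table and listing. No visible analysis uses either duration further, and no hypothesis test is planned in SAP section 8.0, so it would be wrong to infer that a safety, PK or efficacy result changes.

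A reader might also infer that the 40 is miscalculated. Protocol section 1.1.4.5 says "In renal transplant patients, the apparent PK half-life" is 8.5 days, and 5 × 8.5 = 42.5, whereas 40 ÷ 5 = 8.0. The documents cannot show this to be an error. The 8.5 days comes from preliminary modelling of limited data, the half-life predicted for this trial's regimen is blacked out in protocol section 4.1, and the SAP offers the half-lives only as an example. What can be asked is that the half-life be stated.

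**What to change.** - Define duration of administration in the SAP as last dose date minus first dose date plus a stated constant, given for each drug and including rATG. Plus 1 for every drug reproduces the protocol's 5 days for siplizumab, gives 3 for rATG and 337 for a drug taken from Day 0 to Day 336, and needs no dosing interval. If the interval convention is kept, give its value for each drug.
- Name the 40-day window as a separate pharmacological exposure measure, restrict it to siplizumab, and state the half-life behind it.
- Correct protocol section 12.3 in the same way, or record the SAP definition as a departure from it.

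The cost is a few sentences in the SAP, one derivation to reprogram, and the protocol correction or note. The rules use dosing dates, so no new data item is needed.
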